 1. Planar scan of whole body
 2. Planar scan of bilateral hands and wrists
- Clinical labs (after imaging)
- RA-specific labs (after imaging)
- Urinalysis (after imaging)

Visit 9 (Follow-up Telephone Safety Assessment; 5 ± 3 Days After Visit 8)

- Review of concomitant medications
- AE assessment

*If a subject in Arm 3 requires early exit from the study between Week 16 and Week 24, an attempt should be made to complete a final imaging visit and all clinical assessments.

Test Product, Dose, and Mode of Administration:

Tc 99m tilmanocept will be administered through an IV route of injection. A 150-mcg dose containing 10 mCi of Tc 99m will be injected as a slow push into the IV catheter. At the completion of the injection, a 10-mL sterile normal saline flush will be administered. The preferred site of IV placement will be between the elbow and the wrist.

Planned Number of Study Centers:

Up to 10 centers in the United States

Sample Size:

105 evaluable subjects in Arms 1, 2, and 3 as allocated below. Arms 1 and 2 will have N = 38 evaluable subjects per Arm, and Arm 3 will have N = 29 evaluable subjects. A subject is considered evaluable if he/she meets the criteria for the analysis population and has the data necessary for computing the primary endpoint.

Rationale for Sample Size:

The sample size for Arm 1 was determined to provide sufficient data to quantify the precision of TUV in HCs. The sample size of Arm 2 was determined to power a hypothesis test of

$$H_0: \pi \leq 0.80$$

$$H_A: \pi > 0.80$$

at 80%. Here, π represents the fraction of the absolute differences less than 7.5%. The sample size for Arm 3 was determined to set the length of the lower 97.5% confidence limit for Spearman's rank correlation to be no more than 0.15.

After the injection, imaging, and quantitation of a total of 4 subjects in Arms 1 and 2, an interim analysis (interim analysis 1) will be held for the review of quantitative TUV results and assessment of imaging parameters and logistics. A second interim analysis (interim analysis 2) will be held after a total of 30 subjects (≥ 15 RA) in Arms 1 and 2 are injected, imaged, and quantified for the review of intra-and inter-subject TUV variation to contribute to the power analysis of a future Phase 3 study and/or to terminate the study on grounds of data sufficiency.

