9.4 Sample Size Justification

The study will enroll up to 105 evaluable subjects in Arms 1, 2, 3 allocated below, imaged at up to 10 study centers. Arm 1 will have N = 38 evaluable subjects, Arm 2 will have N = 38 evaluable subjects, and Arm 3 will have N = evaluable 29 subjects. A subject is considered evaluable if he/she meets the criteria for the analysis population and has the data necessary for computing the primary endpoint.

The sample size for Arm 1 was determined to assess temporal stability of the 150 mcg tilmanocept mass dose/10 mCi radiolabeling dose. The sample size for Arm 2 was determined to power the hypothesis test at 0.80. The sample size for Arm 3 was determined to provide a lower 97.5% confidence limit for the rank correlation of at most 0.15 when rho = 0.70, using Fisher's Z-transformation methods.

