1.3 Sample Size

Up to 105 subjects from up to 10 study centers will be enrolled into Arms 1, 2, and 3 as allocated below, and imaged. Arm 1 will have N = 38 evaluable subjects, Arm 2 will have N = 38 evaluable subjects, and Arm 3 will have N = 29 evaluable subjects. A subject is considered evaluable if he/she meets the criteria for the analysis population and has the data necessary for computing the primary endpoint.

The sample size for Arm 1 was determined to assess temporal stability of the 150 μ g mass dose/10mCi radiolabeling dose. The sample size for Arm 2 was determined to power a hypothesis test at 0.80:

$$\begin{aligned} H_0: \pi &\leq 0.80 \\ &\text{vs} \\ H_a: \pi &> 0.80, \end{aligned}$$

where π represent the fraction of unsigned differences less than 7.5% The sample size for Arm 3 was determined to provide a lower 97.5% confidence limit for the rank correlation of at most 0.15 when $\rho = 0.70$, using Fisher's Z-transformation methods.

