2.3 Missing Data Conventions

No missing value imputation will be used in this analysis. All analyses will be based on the observed data.

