The Kendall rank correlation between $\Delta TUV_{global[5w]}$ with $\Delta CDAL_{12w}$ and $\Delta CDAL_{24w}$ will be computed and a 95% confidence interval for its value will be computed using Fisher's Z-transformation. Similarly, the Kendall rank correlation between $\Delta TUV_{global[5w]}$ with changes from baseline in DAS28 and in each of the ACR Response Criteria components at weeks 12 and 24 will be computed and a 95% confidence interval for its value will be computed using Fisher's Z-transformation. The marginal distributions of the variables will be characterized with the mean, standard deviation, and the number of data pairs.

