The Kendall rank correlation between $\Delta\text{TUV}_{\text{global}}$ at 5 weeks, $\Delta\text{TUV}_{\text{global}}$ at 12 and 24 weeks with the component parameters of ΔCDAI_{12w} and ΔCDAI_{24w} will be computed and 95% confidence intervals for the values provided using Fisher's Z-transformation. This analysis will be repeated for the correlation between $\Delta\text{TUV}_{\text{global}}$ at 12 and 24 weeks with change in DAS28 and with ACR Response Criteria components at 12 weeks and 24 weeks (Note: the Kendall rank correlation analysis with DAS28 and ACR Response Criteria components at 5 weeks is a primary endpoint, as described above in Section 4.2.1). The marginal distributions of the variables will be characterized with the mean, standard deviation, and the number of data pairs.

Concordance of improvement classification for: 1) $\Delta\text{TUV}_{\text{global}[5w]}$ bucketing; 2) $\Delta\text{TUV}_{\text{global}[5w]}$; 3) $\Delta\text{TUV}_{\text{global}[5w]}$ bucketing with ACPA bucketing; 4) $\Delta\text{TUV}_{\text{global}[12w]}$ bucketing; 5) $\Delta\text{TUV}_{\text{global}[12w]}$; 6) $\Delta\text{TUV}_{\text{global}[12w]}$ bucketing with ACPA bucketing; and 7) ACPA bucketing alone with clinical criteria (ACR Response, CDAL, DAS28, and HAQ-DI) will be analyzed as follows.

ACR Response is derived through a combination of reductions from baseline in swollen or tender joint counts as well as improvement from baseline in at least at least 3 of the other parameters (patient assessment, physician assessment, pain scale, disability/functionality questionnaire, and acute phase reactant [ESR]). This study will evaluate the following three levels of ACR Response:

- ACR20: An ACR20 indicates that 20% improvement is observed in tender or swollen joint counts as well as 20% improvement in at least 3 of the other 5 criteria.
- ACR50: An ACR50 indicates that 50% improvement is observed in tender or swollen joint counts as well as 50% improvement in at least 3 of the other 5 criteria.
- ACR70: An ACR70 indicates that 70% improvement is observed in tender or swollen joint counts as well as 70% improvement in at least 3 of the other 5 criteria.

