		24 Weeks	x.xxx	(x.xxxx, x.xxxx)	xxx	xxxxxx	xxxxxx
Δ CDAI	Overall	5 Weeks	x.xxx	(x.xxxx, x.xxxx)	xxx	xxxxxx	xxxxxx
		12 Weeks	x.xxx	(x.xxxx, x.xxxx)	xxx	xxxxxx	xxxxxx
		24 Weeks	x.xxx	(x.xxxx, x.xxxx)	xxx	xxxxxx	xxxxxx
Δ CDAI	xxxxxx	5 Weeks	x.xxx	(x.xxxx, x.xxxx)	xxx	xxxxxx	xxxxxx
		12 Weeks	x.xxx	(x.xxxx, x.xxxx)	xxx	xxxxxx	xxxxxx
		24 Weeks	x.xxx	(x.xxxx, x.xxxx)	xxx	xxxxxx	xxxxxx
Δ ACR	xxxxxx	5 Weeks	x.xxx	(x.xxxx, x.xxxx)	xxx	xxxxxx	xxxxxx
		12 Weeks	x.xxx	(x.xxxx, x.xxxx)	xxx	xxxxxx	xxxxxx
		24 Weeks	x.xxx	(x.xxxx, x.xxxx)	xxx	xxxxxx	xxxxxx
Δ ADAS28		5 Weeks	x.xxx	(x.xxxx, x.xxxx)	xxx	xxxxxx	xxxxxx
		12 Weeks	x.xxx	(x.xxxx, x.xxxx)	xxx	xxxxxx	xxxxxx
		24 Weeks	x.xxx	(x.xxxx, x.xxxx)	xxx	xxxxxx	xxxxxx

^a Change in ACR will be evaluated through the following components of the ACR Response Criteria: swollen joint count, tender joint count, patient assessment, physician assessment, pain scale, disability/functionality questionnaire, and acute phase reactant (ESR).

^b Kendall rank correlation between Δ TUV at 5 weeks and the indicated measurement and time point.

^c Confidence limits calculated using Fisher's Z-transformation.

If there are no major protocol deviations, then analysis tables for the ITD and PP populations will contain identical results.

STATKING Clinical Services (DD-MMM-YYYY)

Source Program: xxxxxxxx.sas

Table format is repeated for each reader. Entire table (all parts) is repeated for the PP population.

Table 21. Kendall Rank Correlation of Δ TUV, Δ CDAI, Δ ACR Response Criteria Components, and Δ ADAS28 with Δ TUV at 12 Weeks in Arm 3
 Navidea Biopharmaceuticals - Study No. NAV3-31
 ITD Population (N=xxxx)

Part 1 of 3: Reader x

Measure ^a	Component Parameter	Time Point	Kendall Correlation ^b	95% Confidence Limits ^c	n	Mean	Standard Deviation
Δ TUV		12 Weeks	--	--	xxx	xxxxxx	xxxxxx
Δ TUV		24 Weeks	x.xxxx	(x.xxxx, x.xxxx)	xxx	xxxxxx	xxxxxx
Δ CDAI	Overall	12 Weeks	x.xxxx	(x.xxxx, x.xxxx)	xxx	xxxxxx	xxxxxx
		24 Weeks	x.xxx	(x.xxxx, x.xxxx)	xxx	xxxxxx	xxxxxx
Δ CDAI	xxxxxxxxx	12 Weeks	x.xxxx	(x.xxxx, x.xxxx)	xxx	xxxxxx	xxxxxx
		24 Weeks	x.xxx	(x.xxxx, x.xxxx)	xxx	xxxxxx	xxxxxx
Δ ACR	xxxxxxxxx	12 Weeks	x.xxx	(x.xxxx, x.xxxx)	xxx	xxxxxx	xxxxxx
		24 Weeks	x.xxx	(x.xxxx, x.xxxx)	xxx	xxxxxx	xxxxxx
Δ ADAS28		12 Weeks	x.xxx	(x.xxxx, x.xxxx)	xxx	xxxxxx	xxxxxx
		24 Weeks	x.xxx	(x.xxxx, x.xxxx)	xxx	xxxxxx	xxxxxx

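### The Arm 3 Kendall correlations get a Fisher's Z interval with no Kendall variance stated; with the usual standard error, the 95% limits are about 1.3 to 1.5 times too wide at n = 29

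*SAP*

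**What the plan says.** SAP 4.2.1 (Primary Endpoints for Arm 3 Only) opens with "The Kendall rank correlation between" the 5-week change in global TUV and the changes in CDAI at weeks 12 and 24, and states that it "will be computed and a 95% confidence interval for its value will be computed using Fisher's Z-transformation". The same sentence form covers change in DAS28 and in each ACR component. SAP 4.2.2 does the same for the secondary correlations, with "95% confidence intervals for the values provided using Fisher's Z-transformation". Footnote c of the Table 19, 21 and 23 shells reads "Confidence limits calculated using Fisher's Z-transformation". Protocol 9.5.3.3 and 9.5.3.4 use the same method.

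None of these places gives a standard error on the z scale, a variance for Kendall's tau, or a bootstrap for these intervals.

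On size, SAP 1.3 states that "Arm 3 will have N = 29 evaluable subjects". Protocol 9.4 justifies this by a "lower 97.5% confidence limit for the rank correlation of at most 0.15 when rho = 0.70, using Fisher's Z-transformation methods". The protocol synopsis instead refers to the "length of the lower 97.5% confidence limit for Spearman's rank correlation to be no more than 0.15", so it names a different coefficient from the one analysed. SAP 2.3 adds that "No missing value imputation will be used in this analysis", so some correlations may rest on fewer than 29 subjects.

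**The concern.** The familiar Fisher's Z interval is atanh(r) ± 1.96/sqrt(n−3). That standard error belongs to a product-moment correlation. Kendall's tau lies on a different scale and varies less from sample to sample, so the same standard error gives limits that are too wide. The Arm 3 primary endpoints are these correlations, SAP 4.2.1 attaches no test to them, and the interval is their only statement of uncertainty. Arm 3 was also sized on the precision of such a limit. If the interval is miscalibrated, the report would show less precision than 29 subjects actually provide.

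**Working it through.** **Inputs.** n = 29 (SAP 1.3); design correlation 0.70 and distance 0.15 (protocol 9.4, synopsis); two-sided 95% level, so the multiplier is 1.96. The z-scale standard error is not stated, so two forms are compared: Pearson 1/sqrt(n−3), and Kendall sqrt(0.437/(n−4)). The constant 0.437 is an assumption from outside the documents and is checked by simulation below.

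**1. Reproduce N = 29.** With the Pearson form, SE = 1/sqrt(26) = 0.1961 and atanh(0.70) = 0.8673.
- Upper limit: tanh(0.8673 + 1.96 × 0.1961) = 0.849, a distance of 0.149.
- Lower limit: tanh(0.8673 − 0.3844) = 0.449, a distance of 0.251.

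N = 29 is the smallest n with an upper distance of at most 0.15. On the lower side, which the text names, n = 65 would be needed. Other forms give, for the upper and lower side: Spearman with 1.06/(n−3), 30 and 69; Spearman with (1 + r²/2)/(n−3), 35 and 81; Kendall, 16 and 32. Only the Pearson form gives 29.

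**2. Standard errors at n = 29.**
- Pearson form: 0.1961.
- Kendall form: sqrt(0.437/25) = 0.1322; ratio 1.48.
- Exact null variance of tau, 2(2n+5)/(9n(n−1)) = 126/7308 = 0.01724, so SE = 0.1313; ratio 1.49. This does not use the 0.437 constant.

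An interval 1.48 times too wide on the z scale uses a multiplier of 1.96 × 1.48 = 2.90, which corresponds to about 99.6% coverage.

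**3. Intervals on the tau scale.**

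| Observed tau | Pearson form | Kendall form | Width ratio |
|---|---|---|---|
| 0.30 | −0.075 to 0.600 | 0.050 to 0.514 | 1.46 |
| 0.494 | 0.155 to 0.728 | 0.274 to 0.664 | 1.47 |
| 0.70 | 0.449 to 0.849 | 0.543 to 0.810 | 1.50 |

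The row 0.494 = (2/π) × asin(0.70) is the tau that matches rho = 0.70 under bivariate normality. The smallest tau whose interval excludes zero is tanh(1.96 × 0.1961) = 0.367 with the Pearson form and tanh(1.96 × 0.1322) = 0.253 with the Kendall form.

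**4. Simulation, untied bivariate normal data** (20,000 samples of n = 29 per row).

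| True tau | Coverage, Pearson form | Coverage, Kendall form | Excludes 0, Pearson form | Excludes 0, Kendall form |
|---|---|---|---|---|
| 0 | 99.6% | 95.0% | 0.4% | 5% |
| 0.26 | 99.6% | 95.0% | 20% | 54% |
| 0.33 | 99.6% | 94.7% | 40% | 76% |
| 0.41 | 99.5% | 94.5% | 67% | 92% |
| 0.49 (rho 0.70) | 99.6% | 95.0% | 90% | 99% |

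Across the full set of scenarios run, up to tau 0.70, the simulated SD of atanh(tau) was 0.131 to 0.134, close to 0.132.

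**5. Ties and other dependence.** Joint counts, global scores in 0.5-point steps and HAQ-DI will produce ties.
- Heavy ties in one variable: standard error 1.33 to 1.36 times too large; coverage 99.0 to 99.2%.
- Clayton dependence: 1.37 to 1.40 times; coverage 99.1 to 99.4%.
- Heavy-tailed dependence (t, 3 df): 1.27 to 1.30 times.

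Over the tied and heavy-tailed cases, coverage ran from about 98.6 to 99.5%. The Kendall form errs the other way: about 91 to 94% with ties, and 90.7 to 91.8% with heavy tails.

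**6. Fewer subjects.** The ratio of the two forms is 1.48 at n = 25, 1.47 at n = 20 and 1.45 at n = 15, so missing data hardly change it.

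**The case against.** The strongest objection is that the documents never write 1/sqrt(n−3). An interval with a Kendall variance is also a Fisher's Z interval and would fit the SAP wording unchanged. A reader might infer that the plan is shown to apply the Pearson formula; the text supports only that the variance is unspecified. This stands. However, the Pearson form is what the unqualified name suggests, and it is the only form tried that yields N = 29. Left as it is, two programmers could produce limits that differ about 1.5-fold.

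A reader might also infer that real associations will generally look unproven. The documents do not support that. They set no null hypothesis, p-value or success rule for these correlations, and protocol 3.1.3.3 calls the aim a preliminary understanding. At the design value most intervals still exclude zero.

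Nor is this the only Arm 3 inference about 5-week TUV change and response. SAP 4.2.2 gives PPV, NPV and overall accuracy with exact limits, and the Table 44 shell adds p-values for PPV and NPV. These are secondary but do not use this interval.

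Finally, the error is conservative: point estimates are unaffected and false claims of association become rarer. That lowers the severity but does not make the labelled 95% level correct.

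**Conclusion.** The point holds as a calibration fault in the Arm 3 primary intervals, conditional on the Pearson standard error. At n = 29 the interval is about 1.45 to 1.5 times too wide for untied bivariate normal data, with coverage near 99.5%. It is about 1.3 to 1.4 times too wide with ties or non-normal dependence, with coverage of about 98.6 to 99.5%. The consequence is overstated imprecision. An observed tau of about 0.25 to 0.37 would have an interval that includes zero where a calibrated one (untied, bivariate normal case) would not. At the design rho of 0.70, about 90% of intervals exclude zero, against about 98 to 99%. The documents do not show that a trial decision would go wrong. It should be fixed before the final analysis, but it does not undermine the study.

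**What to change.** In SAP 4.2.1 and 4.2.2, footnote c of Tables 19, 21 and 23 (and the PP versions), and protocol 9.5.3.3 and 9.5.3.4, specify Kendall's tau-b with a subject-level bootstrap 95% interval of 5,000 resamples, the number the SAP already uses for RMSD. In a small check on untied data (tau 0.30, n = 29, 400 samples, 600 resamples), a percentile bootstrap covered 95%. Tied data were not part of that check, so a short simulation with tied scores is worth running before the method is fixed. The alternative is a tie-adjusted variance specific to Kendall's tau, written out in full. The form 0.437/(n−4) should not be the default, because it covers only about 91 to 94% with tied scores.

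The coefficient in the sample size text should also match the analysis: the synopsis names Spearman, while protocol 9.4 and SAP 1.3 say only rank correlation. The same edit should state which side of the interval the 0.15 refers to, since 29 comes from the upper side.

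The cost is SAP and protocol wording and minor code; no new data are needed.

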4.2.2 Secondary Efficacy Variables

Secondary Endpoints for Arm 1 only

The normal ranges of TUV_{joint} will be estimated from data collected from healthy subjects (study arm 1) at 60 minutes post-injection. The mean, standard deviation, n (number of joints), and quantile regression estimates of the 5 and 95 percentiles will be provided for shoulder, elbow, wrist, MCP, PIP, and knee. All joints will be summarized individually.

Secondary Endpoints for Arms 1 and 2

The temporal quantitative stability of the images will be assessed by computing the fraction of observations for which $|\Delta TUV_{global}| \leq 0.075$ for the difference between the 60 and 180 minute images. The hypotheses

$$H_0: \pi \leq 0.80$$

vs

$$H_a: \pi > 0.80,$$

where π represent the fraction of unsigned differences less than 7.5% will be tested with an exact test and a Clopper-Pearson (exact) 95% confidence interval for p will be provided. The RMSD will be analyzed by joint, providing 95% confidence intervals for the RMSD using both Normal theory methods and a bootstrap estimate with 5000 bootstrap replications.

The 80th and 90th percentiles of the distribution of unsigned differences will be estimated using quantal regression methods. (These analyses were completed to the sponsor's satisfaction in IA-3.)

Secondary Endpoint for Arm 2 only

Qualitative evaluations of SPECT/CT imaging in localizing tilmanocept uptake will be estimated from the active RA subjects (Arm 2 only) on the joints of the hands and wrists. A frequency table of counts and percent of subjects will be provided.

Secondary Endpoints for Arm 3 only

All RA quantitative assessment variables (CDAI, ACR Response Criteria component scores, DAS28 score, and HAQ-DI) will be summarized by arm, computing the mean, standard deviation, number of observations, minimum, median, and maximum for the observed values at each time point and for the change from baseline for values collected after Day 0. The ACR Response Criteria will be summarized with a frequency table of the highest ACR Response level (None, ACR20, ACR50, ACR70) attained by that subject at that time point. That is, a subject who satisfies ACR50 also satisfies ACR20 but will not appear in the frequency count for ACR20.

The Kendall rank correlation between $\Delta\text{TUV}_{\text{global}}$ at 5 weeks, $\Delta\text{TUV}_{\text{global}}$ at 12 and 24 weeks with the component parameters of ΔCDAI_{12w} and ΔCDAI_{24w} will be computed and 95% confidence intervals for the values provided using Fisher's Z-transformation. This analysis will be repeated for the correlation between $\Delta\text{TUV}_{\text{global}}$ at 12 and 24 weeks with change in DAS28 and with ACR Response Criteria components at 12 weeks and 24 weeks (Note: the Kendall rank correlation analysis with DAS28 and ACR Response Criteria components at 5 weeks is a primary endpoint, as described above in Section 4.2.1). The marginal distributions of the variables will be characterized with the mean, standard deviation, and the number of data pairs.

Concordance of improvement classification for: 1) $\Delta\text{TUV}_{\text{global}[5w]}$ bucketing; 2) $\Delta\text{TUV}_{\text{global}[5w]}$; 3) $\Delta\text{TUV}_{\text{global}[5w]}$ bucketing with ACPA bucketing; 4) $\Delta\text{TUV}_{\text{global}[12w]}$ bucketing; 5) $\Delta\text{TUV}_{\text{global}[12w]}$; 6) $\Delta\text{TUV}_{\text{global}[12w]}$ bucketing with ACPA bucketing; and 7) ACPA bucketing alone with clinical criteria (ACR Response, CDAL, DAS28, and HAQ-DI) will be analyzed as follows.

ACR Response is derived through a combination of reductions from baseline in swollen or tender joint counts as well as improvement from baseline in at least at least 3 of the other parameters (patient assessment, physician assessment, pain scale, disability/functionality questionnaire, and acute phase reactant [ESR]). This study will evaluate the following three levels of ACR Response:

- ACR20: An ACR20 indicates that 20% improvement is observed in tender or swollen joint counts as well as 20% improvement in at least 3 of the other 5 criteria.
- ACR50: An ACR50 indicates that 50% improvement is observed in tender or swollen joint counts as well as 50% improvement in at least 3 of the other 5 criteria.
- ACR70: An ACR70 indicates that 70% improvement is observed in tender or swollen joint counts as well as 70% improvement in at least 3 of the other 5 criteria.

Each subject will be classified as a yes or a no for whether they meet each of the above ACR Response Criteria at each of the applicable post-baseline time points. Note that the above criteria are nested, such that if a subject is a yes for ACR70 at a given time point, then the subject is also a yes for ACR50 and ACR20 for that same time point.

A subject will be classified as improved on the CDAL depending on the baseline score as follows:

- If the baseline value is greater than 22, a reduction of more than 12 will be classified as improved. Otherwise, the subject is not improved.

- If the baseline value is between 10 and 22 (inclusive) a decrease of more than 6 will classified as improved. Otherwise, the subject is not improved.
- If the baseline value is less than 10, a decrease of more than 1 will be classified as improved. Otherwise the subject is not improved.

A subject will be classified as improved on the DAS28 with a score change of greater than 1.2.

A decrease of at least 0.22 in the HAQ-DI will be classified as improved. Otherwise, the subject is not improved on the HAQ-DI.

The $\Delta TUV_{global[5w]}$ values will be used to predict improvement at 12 and 24 weeks according to algorithms 1-3. The $\Delta TUV_{global[12w]}$ values will be used to predict improvement at 24 weeks according to algorithms 4-6. A seventh algorithm based on ACPA bucketing alone will also be applied to predict improvement at 12 and 24 weeks. Algorithms 1-6 will be applied after the change in TUV calculations have been rounded to the nearest integer percentage (i.e., nearest hundredths place for a proportion).

1. $\Delta TUV_{global[5w]}$ bucketing

In the below, TUV_{global} represents the global TUV at the current time point and $TUV_{global[Day 0]}$ represents the global TUV at baseline:

- If $TUV_{global[Day 0]}$ is < 5 then the prediction is N (No improvement)
- Else if

$$\Delta TUV_{global[5w]} = \frac{TUV_{global[5w]} - TUV_{global[Day 0]}}{TUV_{global[Day 0]}} \leq -0.10$$

the prediction is Y (patient has improved). That is, a patient will be predicted as improved if TUV_{global} goes down by greater than or equal to 10%.

- Otherwise, the prediction is N.

2. $\Delta TUV_{global[5w]}$

The TUV_{global} prediction of improvement will also be computed according to the following algorithm:

- If TUV_{global} goes down by greater than or equal to 10%, then predict response
- If TUV_{global} does not go down by 10% or more, then predict no response

3. $\Delta TUV_{global[5w]}$ bucketing with ACPA bucketing

The TUV_{global} prediction of improvement will also be evaluated by combination of the above two algorithms such that:

For patients with TUV_{global} of below 5.0 at baseline:

- ACPA Levels before initiation (at baseline) of the new anti-TNF therapy:
 - ACPA levels ≤ 85 predicts treatment failure (non-response)
 - ACPA level >85 predicts treatment success (significant clinical improvement)

For patients with TUV_{global} at or above 5.0 at baseline:

- If TUV_{global} goes down by greater than or equal to 10%, then predict response (no need to refer to ACPA)
- If TUV_{global} does not go down by 10% or more, then refer to baseline ACPA for prediction:
 - ACPA levels ≤ 85 predicts treatment failure (non-response)
 - ACPA level >85 predicts treatment success (significant clinical improvement)

4. $\Delta TUV_{global[12w]}$ bucketing

In the below, TUV_{global} represents the global TUV at the current time point and $TUV_{global[Day 0]}$ represents the global TUV at baseline:

- If $TUV_{global[Day 0]}$ is < 5 then the prediction is N (No improvement)
- Else if

$$\Delta TUV_{global[12w]} = \frac{TUV_{global[12w]} - TUV_{global[Day 0]}}{TUV_{global[Day 0]}} \leq -0.10$$

the prediction is Y (patient has improved). That is, a patient will be predicted as improved if TUV_{global} goes down by greater than or equal to 10%.

- Otherwise, the prediction is N.

5. $\Delta TUV_{global[12w]}$

The TUV_{global} prediction of improvement will also be computed according to the following algorithm:

- If TUV_{global} goes down by greater than or equal to 10%, then predict response
- If TUV_{global} does not go down by 10% or more, then predict no response

6. $\Delta TUV_{\text{global}[12w]}$ bucketing with ACPA bucketing

The TUV_{global} prediction of improvement will also be evaluated by combination of the above two algorithms such that:

For patients with TUV_{global} of below 5.0 at baseline:

- ACPA Levels before initiation (at baseline) of the new anti-TNF therapy:
 - ACPA levels ≤ 85 predicts treatment failure (non-response)
 - ACPA level >85 predicts treatment success (significant clinical improvement)

For patients with TUV_{global} at or above 5.0 at baseline:

- If TUV_{global} goes down by greater than or equal to 10%, then predict response (no need to refer to ACPA)
- If TUV_{global} does not go down by 10% or more, then refer to baseline ACPA for prediction:
 - ACPA levels ≤ 85 predicts treatment failure (non-response)
 - ACPA level >85 predicts treatment success (significant clinical improvement)

7. ACPA bucketing alone

The following will be used to predict improvement solely on the basis of ACPA:

- ACPA baseline level ≤ 85 predicts treatment failure (non-response)
- ACPA baseline level >85 predicts treatment success (significant clinical improvement)

For each of the RA improvement criteria, a cross-classification table will be provided. The Uncertainty coefficient for the clinical criterion given the $\Delta TUV_{\text{global}[5w]}$ of $\Delta TUV_{\text{global}[12w]}$ classification and its standard error will be calculated. The positive predictive value (PPV), negative predictive value (NPV), and overall accuracy (OA) will be calculated and 95% exact (Clopper-Pearson) confidence intervals will be provided.

PPV and NPV will be calculated as follows, where $\Delta TUV_{\text{global}[XXw]}$ is either $\Delta TUV_{\text{global}[5w]}$ or $\Delta TUV_{\text{global}[12w]}$, as appropriate:

Clinical Criterion Classification			
$\Delta TUV_{global[XXw]}$ and/or ACPA Classification	Improved	Not Improved	Total
Improved	A	B	A+B
Not Improved	C	D	C+D
Total	A+C	B+D	A+B+C+D

$$PPV = A/(A+B)$$

$$NPV = D/(C+D)$$

$$OA = (A+D)/(A+B+C+D).$$

A separate table will be provided to summarize the baseline ACPA levels on a continuous scale and the number and percentage of subjects in each ACPA category (≤ 70 , > 70).

Figures displaying the ΔTUV_{global} by time point (5, 12, and 24 weeks) will be created to display the relationship between ΔTUV_{global} over time with the corresponding clinical response assessment (ACR20/50/70, DAS28, and CDAI) at the given time point.

